3. GENERAL STATISTICAL CONSIDERATIONS

3.1. Randomization and Analytic Cohorts (The process is described in detail in the protocol)

Weeks when the MSU is available or not are randomly selected. Stroke events are orthogonal to whether the MSU was being deployed or not that week and thus participants will be randomly

entered into either the MSU or SM groups depending on when their stroke occurs.

The primary analytic cohort is based on a modified intention-to-treat (ITT) analysis where the subject will be assigned to the group that they were enrolled in (e.g. if a patient was enrolled using SM, they would be assigned to the SM group) and adjudicated (by the blinded adjudicator) to be tPA eligible. The usual ITT includes every subject who is randomized according to randomized treatment assignment. In this study, all patients within each group who are adjudicated as tPA eligible by an adjudicator blinded to group assignment are included. The randomized assignment is not conducted for each patient, rather we generally alternated weeks to be either MSU or SM weeks, which is independent of when a subject randomly has a stroke and calls 911. Therefore, this may be considered a cluster-randomized trial where the cluster is the days when the MSU is available and the other cluster is when MSU is not available. There is not anything clinically important to set the cluster of when the MSU was available or not as a week (e.g., an alternative design could set one week as having MWF as MSU days and TTH as SM days and the next week as the opposite), but this made it convenient to set work schedules and to have a similar amount of time dedicated to recruitment of MSU and SM subjects and there is not a scientific nor statistical rationale suggesting that the clusters would be related to the patient's outcomes and intervention effect. Patients are, in a sense, "randomly" allocated into the clusters based entirely on when they happen to have their stroke in relation to the prospectively determined cluster allotment of whether the MSU is available or not. Furthermore, in order to optimize the utilization of the MSU, some cities have 2 sites enrolling patients at the same time, with one site running the MSU and other enrolling SM patients and then they switch the next week.

There are a few cases when the MSU was not available during an "MSU week" (e.g. the unit is out of service on another call, had to be serviced for an oil change, staff were sick and therefore unable to come in) and stroke patients that were treated using standard management were enrolled into the study by the study team into the SM arm. These few subjects will be included in the primary analysis in the SM arm, but moved to the MSU arm in a sensitivity analysis (see section 5.1.3). The decision to include them in the primary analysis is based on a November, 2019 comparison of the SM subjects who were enrolled during an "MSU week" compared to the SM subjects enrolled during an "SM week". Baseline characteristics (age, sex, ethnicity, race, pre-stroke mRS, baseline NIHSS, tPA treatment, time from LSN to tPA bolus, endovascular treatment, and DTGP) were similar between the groups, confirming our belief that there should not be any added bias for including them in the primary analysis. The benefit of including them is to improve the MSU:SM ratio and to increase the chance of recruiting subjects according to the projected timeline. However, this analysis will be repeated at the end of the study to confirm that no significant differences exist between these two SM populations before including them in the MSU arm.

In response to peer review, post hoc analyses were added to look at two additional cohorts: (1) all enrolled, regardless of adjudication; (2) all adjudicated enrolled, excluding hemorrhages.

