
5.L. Avoiding bias. We aim to carry out a prospective randomized cluster trial with MSU or SM deployment weeks and blinded assessment of both trial entry as well as clinical outcomes. The ideal study design to test efficacy of MSU vs. SM stroke treatment would be a randomized clinical trial with patient as the unit of randomization. In the latter design, treatment assignment (MSU or SM pathway) would happen in a randomized fashion either at the time of 911 call or after arrival on-scene when many stroke mimics or false-alarms can be ruled out. However in both these scenarios, the MSU would need to be available and deployed on each and every possible stroke call. Unfortunately, this design is not feasible since we have only a single MSU and staffing the unit 7 days a week every week has been cost-prohibitive to date. Also, on SM weeks neither the UT CPHS nor EMS will allow us to arrive on-site with the MSU and not utilize it if the patient is having a stroke. Therefore, on non-MSU dispatch weeks (SM weeks), the MSU team is still dispatched but travels in a private vehicle.

A valid criticism of such a cluster randomized trial is that bias can be introduced through differential recruitment across treatment groups. We have introduced several design features into our pragmatic study to reduce the potential for bias due to lack of allocation concealment. All potential stroke patients will be identified by a 911 dispatch center adhering to current standard of care protocols. All patients will be subsequently screened for trial enrollment at the same pre-hospital time by the same investigators on both MSU and SM weeks to ensure that comparisons are made between similar patients.

For all patients enrolled, criteria for study enrollment and tPA treatment will be subsequently reviewed by a VN blinded to MSU vs SM assignment and not otherwise involved in study management or analysis. The blinded VN determines from a dedicated "adjudication form", omitting any time data or other information that would produce unblinding, if the patient meets criteria for study enrollment and for tPA treatment. If the patient is enrolled or considered a "tPA-eligible patient" on either MSU or SM weeks, but do not meet criteria after adjudication, they will not be included in data analysis of the primary outcome. If an enrolled patient meets criteria for tPA after adjudication, but is not treated, that

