4. SAMPLE SIZE DETERMINATION

4.1. Sample Size for the Phase III trial

The power of this trial was based on the difference in primary outcome, 90 d uw-mRS. Based on preliminary data, we expected 1.8 times as many MSU as SM patients because when we began the study, on SM weeks some patients were occasionally taken by EMS to non-participating stroke centers where they could not be enrolled into the study. On MSU weeks, these patients would be transported in the MSU only to participating hospitals and therefore enrolled. Subsequently, we have incorporated these non-participating hospitals into the study, thereby mitigating this gap and the groups are now balanced. With a sample size of 693 total tPA-eligible patients (446 MSU and 247 SM patients, assuming 10% lost to follow-up [LTF]), the study will have 80% power with a 0.05 Type I error to detect a difference between groups of 0.09 in the mean uw-mRS using a two-sample t-test. This difference is plausible and important. In a re-analysis of 11 acute stroke studies⁸, the difference in mean 90d uw-mRS between groups ranged from 0.024-0.25, with most positive trials in the range of 0.1. In the NINDS tPA trial, 90d uw-mRS difference was 0.09 between tPA and placebo.

In March, 2018, [name], blinded to study data, requested, and PCORI approved, an increased sample size to 1095 patients from the 693 initially requested, and to allow three additional sites to be added. This request was based on our reassessment of anticipated difference in 90 day uw-mRS based on a.) results of the Berlin non-randomized study which showed a 0.07 difference between MSU and control patients, b.) results of the DAWN trial which was the first completed study to use the uw-mRS, and c.) reanalysis of a substantial number of completed stroke trials where conventional mRS outcomes were translated to uw-mRS (see figure below). In that analysis, Broderick et al found that the smallest clinically meaningful difference was 0.04¹. We based our initial sample size of 693 tPA eligible patients on the ability to detect a 0.09 point difference which was the same as between tPA and placebo in NINDS. The endovascular studies found a >0.10 point difference. Based on these pieces of information which were not available when we designed our study, [name] reassessed

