5.1.2. Primary Clinical Analysis

The mean uw-mRS at 90d along with corresponding two-sided 95% confidence intervals will be compared between groups using a two-sample t-test or Wilcoxon rank sum test if the assumption of normality does not hold. Although the mRS is an ordinal outcome, the difference between the uw-mRS categories has clinical significance and the t-test assumption and central limit theorem are likely satisfied. The primary analysis of uw-mRS will be adjusted for baseline uw-mRS, site, any baseline covariates that are different between the two groups, and covariates associated with mRS, including baseline NIHSS, age, pre-morbid mRS, and previous TIA/stroke, in a linear regression model. If the assumptions of the model are not satisfied, a restricted cubic spline will be used to model baseline continuous variables (NIHSS and age). If the linear regression with splines does not fit well, we will use ordinal logistic regression to adjust for the variables. If the proportional odds assumption fails, we will use logistic regression with mRS 0-1 vs 2-6 as the primary analysis. Assuming that the primary analysis doesn't use the following models, sensitivity analyses of the primary outcome will be conducted including ordinal (shift) analysis using a proportional odds model and proportion achieving a dichotomized outcome of mRS 0-1 vs 2-6 using binary logistic regression.

In response to peer review, we added post-hoc propensity score analyses using propensity scores as an alternative way to reduce any effects of confounding to estimate the effect of MSU group on dichotomized mRS (0-1 versus 2-6). The individual propensities for enrolling into the MSU versus EMS groups were estimated using a separate selection multivariable logistic regression model with variables site, baseline NIHSS, pre-stroke

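### Allocation is by deployment week, but the sample size and every MSU-versus-SM analysis treat patients as independent; the likely effect is small and the repair cheap.

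*SAP*

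**What the plan says.** Protocol 5.L states the design: "We aim to carry out a prospective randomized cluster trial with MSU or SM deployment weeks". SAP 3.1 agrees on the unit: "The randomized assignment is not conducted for each patient, rather we generally alternated weeks to be either MSU or SM weeks". It adds that "this may be considered a cluster-randomized trial where the cluster is the days when the MSU is available".

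The same section explains the choice of a week as a matter of convenience for work schedules and of similar recruitment time in each arm. It then sets clustering aside because "there is not a scientific nor statistical rationale suggesting that the clusters would be related" to the patients' outcomes or the intervention effect.

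The sizing in SAP 4.1 uses a two-sample t-test for 0.07 on the utility-weighted mRS, with SD 0.385, a 3:2 ratio and 5% loss, and arrives at 1038. It mentions neither an ICC nor a design effect.

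SAP 5.1.2 says mean outcomes are "compared between groups using a two-sample t-test or Wilcoxon rank sum test if the assumption of normality does not hold". It then makes the primary analysis a linear regression adjusted for site and baseline covariates. The fallbacks are splines, ordinal logistic and binary logistic regression. The post hoc weighted analyses (5.1.2), the sensitivity analyses (5.1.3) and the missing-data plan (5.1.6) add no week random effect, no GEE and no cluster-robust variance.

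**The concern.** Inference should follow the unit that was allocated. If outcomes of patients from the same location and week are positively correlated, independent-patient standard errors are too small. The primary confidence interval is then too narrow and the test rejects a true null more often than 5%.

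That strokes fall into weeks by chance supports comparable groups. It does not make outcomes within a week independent. Shared staffing or calendar-time effects could link them. The documents do not state that they do, so this is an assumption. The gap is that the plan takes the correlation to be zero and never looks.

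The presentation also invites challenge. SAP 7.2 commits to the standard CONSORT checklist, while the footnote to the SAP's own Appendix A points to the extension for cluster trials.

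**Working it through.** **Inputs.** From SAP 4.1: difference 0.07, SD 0.385, ratio 1.5, loss 5%, N = 1038. Power of 80% and type I error of 0.05 are stated there for the earlier target of 693 ("the study will have 80% power with a 0.05 Type I error to detect") and are assumed to carry over. Two-sided testing is inferred from SAP 5.1.2.

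**Step 1: the plan's figure.** With no clustering,

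n(SM) = (1 + 1/1.5) x [0.385 x (1.960 + 0.842)/0.07]² = 395.7; total = 2.5 x 395.7 = 989.3 evaluable.

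For 5% loss, 989.3/0.95 = 1041.4 and 989.3 x 1.05 = 1038.75. The stated 1038 therefore reproduces closely with a design effect of 1.0. At 1038 x 0.95 = 986 evaluable, two-sample t power is 79.8%.

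**Step 2: patients per cluster.** The allocated unit is the location-week, since some cities run MSU in one location and SM in the other during the same week.

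- Early randomised Houston (Protocol 4.D): 45 tPA-treated patients in 27 weeks, about 1.7 per week. This counts treated patients as the nearest available figure to eligible ones.
- Houston yearly rate, one unit (Protocol 5.J): 70/52 = 1.35.
- Houston with a second location (Protocol 5.J): 90 per year over two locations, 90/104 = 0.87.
- New sites (enrolment projections in the Protocol): 1 to 2 per month, 12/52 = 0.23 to 24/52 = 0.46.

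**Step 3: design effect.** With cluster sizes that vary, DE = 1 + (E[m²]/E[m] - 1) x ICC. For Poisson counts E[m²]/E[m] = m + 1, so DE = 1 + m x ICC. The ICC range of 0.01 to 0.05 is an assumption.

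**Step 4: consequences.** Actual type I error = 2[1 - Φ(1.96/√DE)]. Power is the two-sample t power at 986/DE. Each cell runs from ICC 0.01 to ICC 0.05.

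| Patients per location-week | DE | Type I error | Power |
|---|---|---|---|
| 1.7 | 1.017-1.085 | 5.2-6.0% | 79.1-76.5% |
| 1.35 | 1.014-1.068 | 5.2-5.8% | 79.3-77.2% |
| 0.87 | 1.009-1.044 | 5.1-5.5% | 79.5-78.1% |
| 0.46 | 1.005-1.023 | 5.1-5.3% | 79.6-78.9% |
| 0.23 | 1.002-1.012 | 5.0-5.1% | 79.7-79.3% |

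In the worst cell the standard error is understated by √1.085 - 1, about 4%. With equal cluster sizes at 1.7 per week, DE = 1 + 0.7 x ICC. Type I error is then 5.1-5.4% and power 79.5-78.4%.

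**The case against.** **It was a considered choice.** SAP 3.1 explains why weeks were used and why clustering was judged ignorable. That is so, and this is not an oversight. The reason given is still an assertion, with no planned estimate or check behind it.

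**Site is already in the primary model, and weeks generally alternate.** Both points stand. Site adjustment removes between-site correlation, and alternation largely balances slow seasonal trends between the arms. Only correlation specific to a location-week, remaining after site and covariates, matters. The design-effect formula ignores these protections, so the table probably overstates the inflation.

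**The effect is small.** Agreed. The 1.7 rate is the highest in the documents and should not be applied to the whole trial, and no document supports an ICC as large as 0.05.

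**No mechanism is documented.** A reader might infer from the remark about work schedules that patients in one week share the same crew and neurologist. The text does not say so. Protocol 5.C.1 describes ten-hour cover seven days a week, and 5.K refers to shifts. Protocol 5.C.3 allows faculty, fellows or an on-call remote neurologist. Protocol 5.C.4 leaves SM treatment to the hospital stroke team.

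**The repair does not fit every test.** Also correct: Wilcoxon and Fisher tests have no robust-variance option, and some SM patients were enrolled in MSU weeks, so a week can hold both arms. The fix has to allow for both.

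**Conclusion.** The point holds as a mismatch between the declared design and the specified inference. Its expected effect is modest: type I error of about 5.0-5.5% and power of 79.7-78.1% at 0.23 to 0.87 patients per location-week, and 5.2-6.0% with 79.1-76.5% at the busiest rate. These figures rest on an assumed ICC of 0.01 to 0.05, Poisson counts and no allowance for covariates.

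A reader might infer that 1038 is materially too small. The documents do not support that. The figure reproduces from its stated inputs, and clusters of roughly 0.2 to 1.7 patients leave little room for inflation. A reader might also take the SAP's description of the cluster as available versus unavailable days to mean that there are only two clusters. The allocation text makes the unit the week, and in two-location cities the location-week.

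The change is worth making because it costs little and brings the analysis into line with the unit allocated.

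**What to change.** - **SAP 5.1.2:** specify cluster-robust standard errors, clustered on location-week, for the primary linear regression. Do the same for the other MSU-versus-SM regression models (linear, ordinal, logistic and Cox).
- **SM patients enrolled in MSU weeks:** keep them in the location-week in which they were enrolled. A robust variance accepts clusters that contain both arms.
- **Reporting:** give the estimated location-week ICC for the primary outcome.
- **Wilcoxon and Fisher tests:** keep them as supporting analyses, labelled as not adjusted for clustering.
- **SAP 3.1:** define the cluster as the location-week. Replace the sentence denying a rationale with a statement that within-week correlation is allowed for.

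No change to the sample size is needed. Even at 1.7 per week, 1038 patients span about 1038/1.7 = 610 location-weeks, so there are ample clusters for a robust variance. The cost is SAP wording, a cluster option in each regression model, and slightly wider confidence intervals.

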3.2. Blinding

Blinded assessment of both trial entry, tPA-eligibility, and study outcomes. All patients are screened for trial enrollment during their pre-hospital evaluation and management by the same investigators

on both MSU and SM weeks to ensure that comparisons are made between similar patients, using similar criteria, at a similar stage of illness. For enrolled patients, criteria for study enrollment and tPA treatment are subsequently reviewed by a vascular neurologist (VN) blinded to MSU vs SM assignment and not otherwise involved in study management or analysis. The blinded VN determines from a dedicated “adjudication form”, omitting any time data or other information that would produce unblinding, if the patient meets criteria for study enrollment and for tPA treatment. For comparing outcomes between MSU and SM, we will only include tPA-eligible patients on both MSU and SM weeks, whether or not actually treated, based on this blinded review. Investigators obtaining all outcomes are blinded to treatment allocation.

3.3. Multiplicity

No adjustments for multiple comparisons will be made. However, the secondary analyses will be interpreted with caution.

4. SAMPLE SIZE DETERMINATION

4.1. Sample Size for the Phase III trial

The power of this trial was based on the difference in primary outcome, 90 d uw-mRS. Based on preliminary data, we expected 1.8 times as many MSU as SM patients because when we began the study, on SM weeks some patients were occasionally taken by EMS to non-participating stroke centers where they could not be enrolled into the study. On MSU weeks, these patients would be transported in the MSU only to participating hospitals and therefore enrolled. Subsequently, we have incorporated these non-participating hospitals into the study, thereby mitigating this gap and the groups are now balanced. With a sample size of 693 total tPA-eligible patients (446 MSU and 247 SM patients, assuming 10% lost to follow-up [LTF]), the study will have 80% power with a 0.05 Type I error to detect a difference between groups of 0.09 in the mean uw-mRS using a two-sample t-test. This difference is plausible and important. In a re-analysis of 11 acute stroke studies⁸, the difference in mean 90d uw-mRS between groups ranged from 0.024-0.25, with most positive trials in the range of 0.1. In the NINDS tPA trial, 90d uw-mRS difference was 0.09 between tPA and placebo.

In March, 2018, [name], blinded to study data, requested, and PCORI approved, an increased sample size to 1095 patients from the 693 initially requested, and to allow three additional sites to be added. This request was based on our reassessment of anticipated difference in 90 day uw-mRS based on a.) results of the Berlin non-randomized study which showed a 0.07 difference between MSU and control patients, b.) results of the DAWN trial which was the first completed study to use the uw-mRS, and c.) reanalysis of a substantial number of completed stroke trials where conventional mRS outcomes were translated to uw-mRS (see figure below). In that analysis, Broderick et al found that the smallest clinically meaningful difference was 0.04¹. We based our initial sample size of 693 tPA eligible patients on the ability to detect a 0.09 point difference which was the same as between tPA and placebo in NINDS. The endovascular studies found a >0.10 point difference. Based on these pieces of information which were not available when we designed our study, [name] reassessed

the anticipated difference between groups if the MSU produces a substantial reduction in time to treatment, and felt that a difference of 0.07 is a more realistic goal. [name] did not participate in that decision since he is unblinded.

Assuming a 3:2 (1.5) imbalance, 5% LTFU, and using the pooled standard deviation of STEMO & No STEMO group ($sd=0.385$), numbers of patients needed to detect a difference of 0.07 using a 2-sample t-test is $N=1038$. Our LTFU so far has been around 5% so we expect this assumption to be reasonable. PCORI has agreed to the increase in sample size and sites sufficient to detect a 0.07 difference.

[figure not shown]

Figure. Reanalysis of a substantial number of completed stroke trials where conventional mRS outcomes were translated to uw-mRS. Effect sizes reported. From Broderick, et al.

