- **5.I.** Concomitant therapy. All treatments are given according to standard of care protocols or published guidelines. Off-protocol unapproved treatments are not allowed. The use of intra-arterial thrombectomy (IAT) is allowed in this study but follows published guidelines, e.g. patients with carotid T, M1, A1, proximal M2, or basilar occlusions on screening vascular studies, and groin puncture within 6 hours (4 hours prior to 2/16/15) of symptom onset following curent guidelines¹⁸ (see Appendix 3). To date, about 17% of MSU tPA treated patients have received IAT. Although this number is relatively small, we recognize the possibility of "collider bias" in interpreting MSU vs SM results in the subgroup of patients undergoing IAT (see Potential Biases section 13). Conceivably, MSU pts will need less IAT if they respond to earlier tPA, or, if they need IAT, MSU pts may get it faster due to earlier warning, so that better outcomes in those patients may be due to earlier IAT and not directly due to earlier tPA treatment. Also, benefit from IAT in SM patients may obscure the positive effect of the MSU intervention. While these considerations may confound interpretation of the results, they should not

prevent us from determining if MSU has a beneficial effect if added to background therapy. Considering that IAT is now considered background therapy, the main impact of IAT will be on the expected 90 day mRS and therefore the power/sample size. A sensitivity analysis will be carried out both including and excluding patients receiving IAT.

5.J. Recruitment and Retention Plan. We calculate that we will be able to recruit enough patients to answer the Specific Aims. We already implemented our first recruitment stimulus by arranging to rendezvous with EMS units bringing stroke patients to the Texas Medical Center (TMC) from beyond our 5-10 mile (radius) catchment area. Transport of some patients to the CSCs from beyond 5-10 miles and paramedic rendezvous are already part of routine EMS practice policy and does not involve "re-routing" of patients for this study.

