Another bias might be introduced by the confounding effects of concommitant therapies such as endovascular treatment (IAT). We will try to achieve standardized management by only admitting patients to a certified stroke center and VN service, by direct discussion of expected management between the VN team and the MSU team at the time of admission, by feedback from our RN who will be visiting the patients regularly during the first few days, and by asking these teams to adhere to published guidelines for stroke management^{1,19}. Regarding IAT, recent clinical trials of IAT¹⁴⁻¹⁷ have shown striking and consistent benefit in patients with severe strokes (median NIHSS 17, IQ 12-21). who have persisting large artery occlusion in the anterior circulation after receiving IV tPA, have small core infarcts on CT scan, were treated with the latest stentrievers, and had groin puncture at ~3.5-4 hours post onset. To date, 17% of our MSU tPA treated patients have received IAT, all of whom met criteria for IAT following criteria in recently published guidelines for IAT¹⁹. We expect that this percent will increase somewhat as clinical practice responds to additional data from these trials. All CSCs participating in this study will offer IAT according to published guidelines¹⁹, and as new data become available and incorporated into guidelines, we will incorporate them into the BEST-MSU trial. Shortening the time from LSN to start of IAT may be an important advantage to the MSU. However, we recognize that earlier treatment on the MSU might lead to more tPA success and therefore fewer IAT treatments in the MSU arm. Conversely, MSU management might increase the use of IAT by allowing more patients to be treated within the time window of possible IAT efficacy. Finally, SM patients may benefit from IAT obscuring some of the benefit of the MSU intervention. Since patients managed by either MSU or SM will have comparable access to IAT, any difference in the frequency of IAT between the arms would be a consequence of the effect of MSU vs SM management, and therefore will be important to measure and factor into our analysis. However, we will not be able to adjust for postintervention IAT management, but rather need to consider it as part of "background therapy" in this trial that compares MSU + background therapy to SM + background therapy. To explore any confounding effect, we will present descriptive statistics of IAT treatment in both arms and conduct sensitivity analyses, including a time-dependent covariate for IAT in the Cox model for mortality, using propensity score anlaysis of who received IAT in the analysis of 90-day mRS, and subset analyses including/excluding IAT patients.

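### The primary model has no calendar-time term although the MSU:SM ratio and stroke care are both described as changing during the trial; the possible bias is small and cheap to remove

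*SAP*

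**What the plan says.** **Model.** SAP 5.1.2: "The primary analysis of uw-mRS will be adjusted for baseline uw-mRS, site, any baseline covariates that are different between the two groups", together with baseline NIHSS, age, pre-morbid mRS and previous TIA or stroke. No enrolment date, year or period is named there, in the post hoc propensity model, or among the subgroups in SAP 5.1.5. The only analysis tied to calendar time is in SAP 5.1.3, which drops patients enrolled in the COVID-19 months.

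**Arm ratio.** SAP 4.1: "we expected 1.8 times as many MSU as SM patients because when we began the study", because some SM patients were taken to hospitals outside the study. The section continues: "Subsequently, we have incorporated these non-participating hospitals into the study, thereby mitigating this gap and the groups are now balanced". The revised sample size in the same section is nevertheless computed at a different ratio: "Assuming a 3:2 (1.5) imbalance, 5% LTFU". The revised justification in Protocol 7.D also reports better balance than first planned and also uses 1.5. SAP 3.1, referring to a November 2019 comparison, still gives a better ratio as a reason for keeping in the SM arm those SM patients who were enrolled during MSU weeks.

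**Care.** Protocol 5.I gives the thrombectomy window as "groin puncture within 6 hours (4 hours prior to 2/16/15) of symptom onset". Protocol 5.L, noting that 17% of MSU tPA-treated patients had received thrombectomy, adds: "We expect that this percent will increase somewhat as clinical practice responds to additional data from these trials". Protocol 5.C.3 lets a remote neurologist replace the on-board one for blocks of time.

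**The concern.** MSU and SM weeks generally alternate (SAP 3.1), which balances weeks between the arms. It does not balance patients per week. If early MSU weeks yielded more patients relative to SM weeks than later ones did, MSU patients are enrolled earlier on average. Any trend in outcome common to both arms then enters the arm contrast, with a sign that favours the arm enrolled later.

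The site term absorbs level differences between early and late sites. It cannot absorb a trend inside one site whose own ratio changed. Houston is where that matters most: it was the only site until Colorado and Memphis began enrolling in September 2016 (Protocol milestones), so the conditions at the start of the study are Houston's. At stake is some attenuation and loss of power on the primary endpoint.

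**Working it through.** **1. The plan's own figure.** Inputs from SAP 4.1: difference 0.07, SD 0.385, ratio 1.5, 5% loss. Two-sided alpha 0.05 and 80% power are stated for the initial sample size and assumed to carry over.

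SM patients = (1 + 1/1.5) × (1.960 + 0.842)² × 0.385² / 0.07² = 396; MSU = 594; total 990. Dividing by 0.95 gives 1043; multiplying by 1.05 gives 1040. The stated 1038 is reproduced to within rounding.

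**2. Bias formula.** With two periods, no time term and no site term:

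bias = drift × (share of MSU patients enrolled late − share of SM patients enrolled late).

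The documents give neither drift nor a switch point. Assumed: drift of 0.02, 0.05 or 0.10 uw-mRS, and 150, 346, 519 or 693 of the 1038 enrolled before the ratio changed. Two ratio paths are taken: 1.8 to 1.0 (reading SAP 4.1 literally), and 1.8 early with 1.5 overall (the sizing ratio).

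| Path | Enrolled early | Gap in late share | Bias, drift 0.02 | Bias, drift 0.05 | Bias, drift 0.10 |
|---|---|---|---|---|---|
| 1.8 to 1.0 | 150 | −0.071 | −0.0014 | −0.0035 | −0.0071 |
| 1.8 to 1.0 | 346 | −0.128 | −0.0026 | −0.0064 | −0.0128 |
| 1.8 to 1.0 | 519 | −0.146 | −0.0029 | −0.0073 | −0.0146 |
| 1.8 to 1.0 | 693 | −0.132 | −0.0026 | −0.0066 | −0.0132 |
| 1.8, overall 1.5 | 150 | −0.026 | −0.0005 | −0.0013 | −0.0026 |
| 1.8, overall 1.5 | 346 | −0.060 | −0.0012 | −0.0030 | −0.0060 |
| 1.8, overall 1.5 | 519 | −0.089 | −0.0018 | −0.0045 | −0.0089 |
| 1.8, overall 1.5 | 693 | −0.119 | −0.0024 | −0.0060 | −0.0119 |

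Check of the largest gap (half early, 1.8 to 1.0): the early share is 0.643/(0.643 + 0.5) = 56.25% in MSU and 0.357/(0.357 + 0.5) = 41.7% in SM, a gap of 14.6 points.

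**3. With the site term.** One illustration. Protocol 5.J projects about 150 Houston patients in two years, then about 90 a year for three: 150 + 270 = 420 of 1038. Assume Houston moved from 1.8:1 to 1:1 after the first 150, and the other 618 were 1:1 throughout.

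- Houston MSU: 96.4 early + 135 late = 231.4. Houston SM: 53.6 early + 135 late = 188.6.
- Late shares 0.583 and 0.716; gap −0.133.
- In a site-adjusted model each site is weighted by n × p × (1 − p): Houston 420 × 0.551 × 0.449 = 103.9; others 618 × 0.25 = 154.5; Houston weight 0.402.
- Net imbalance −0.133 × 0.402 = −0.053. Switching after 285 Houston patients instead gives −0.051.
- Bias −0.001, −0.003 and −0.005 at drift 0.02, 0.05 and 0.10. The last two are about 4% and 8% of 0.07.
- With 5% loss the arms are 513 and 473, and SE = 0.385 × √(1/513 + 1/473) = 0.0245. Power for a true 0.07 falls from 81% to 78% (drift 0.05) or 75% (drift 0.10).

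**4. Cost of a period term.** The variance inflation is 1/(1 − R²), with R² from regressing arm on period. Across the eight rows above, R² is 0.0013 to 0.0208, so the cost is 0.1% to 2.1% of effective sample size and under 1 point of power.

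**The case against.** The case against is strong on size.

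- **The ratio path is not documented.** The 1.8:1 is an expectation from preliminary data, not an observed early ratio. Balance in SAP 4.1 sits badly with the 1.5 used for sizing and with SAP 3.1. Protocol 7.D gives another cause for 1.8:1, namely that first responders alert the team more readily on MSU weeks, which adding hospitals would not remove. A reader might infer that MSU patients are known to come disproportionately from the early years. The documents do not show that.
- **The drift has no source.** A value of 0.10 exceeds the tPA-versus-placebo difference of 0.09 quoted in SAP 4.1. If thrombectomy use rose by 10 points (assumed), with a gain of 0.10 to 0.25 per treated patient (magnitudes mentioned in SAP 4.1), drift would be 0.010 to 0.025. Even with the 0.146 gap, the bias is then 0.0015 to 0.004, or 2 to 5% of 0.07.
- **The dated criteria change came very early.** February 2015 is about 26 weeks into randomisation. Protocol 4.D counts 45 tPA-treated patients in the first 27 weeks, and 45/1038 is about 4%. Telemedicine alters only the MSU arm, so it is a change in the intervention rather than a trend shared by both arms.
- **Other protections exist.** Some sites run both arms in the same week at two locations, case-mix covariates are in the model, and thrombectomy sensitivity analyses are planned. The clause on covariates that differ between groups could also bring in period. At 986 evaluable patients a 12.8-point gap gives a chi-square of 986 × 0.0183 = 18, but a 6-point gap gives only 986 × 0.0038 = 3.7, just short of 3.84.

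All of this limits the magnitude. It does not fill the gap: enrolment date is not named as a variable to be tested, selection by observed difference can miss modest imbalance, and a site term cannot remove a trend within Houston.

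**Conclusion.** The concern holds as an omission with a small, conditional consequence. The plan describes a shifting arm ratio and changing care, and leaves calendar time out of the primary model. The possible bias is roughly 0.001 to 0.015 uw-mRS across the assumed ranges. It is most plausibly about 0.005 or less once site is in the model, which is under about 8% of the 0.07 target. Both figures rest on assumed drift, switch points and ratio paths. The larger one also ignores site adjustment and is closer to an upper bound.

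Two stronger readings should be resisted. A reader might conclude that secular trends are known to contaminate the estimate; the documents show only that they could. A reader might also fear a manufactured MSU benefit. On the described ratio path, improving outcomes would bias against MSU, and a spurious benefit would require outcomes to worsen over time.

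**What to change.** - Add enrolment period (calendar year, or site-by-period where numbers allow) to the linear, ordinal and logistic models in SAP 5.1.2. SAP 5.1.2 already contains analyses added after peer review, so if outcomes are unblinded, leave the primary model as it is and report the period-adjusted model as a sensitivity analysis labelled post hoc.
- Report MSU and SM counts by site and year, so that readers can see whether the ratio moved and where.
- Reconcile the statement in SAP 4.1 that the groups are balanced with the 1.5 ratio in SAP 4.1 and Protocol 7.D, and with the wish in SAP 3.1 to improve the ratio.

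The cost is a few degrees of freedom, about 0.1 to 2% of effective sample size for a two-period term; site-by-period uses more. Enrolment date must already be available, since the COVID-19 sensitivity analysis depends on it. A period term does not correct the differential recruitment given as the reason for the imbalance (SM patients taken to non-participating hospitals, or fewer alerts on SM weeks); that needs separate treatment.
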